Medtronic, EC/IRB or Regulatory Authority may decide to suspend or prematurely terminate an investigation site (e.g. in case of expiring approval of the reviewing EC/IRB, non-compliance to the Clinical Investigation Plan or lack of enrollment). If an investigation site is suspended or prematurely terminated, Medtronic shall promptly inform the clinical investigator(s) of the termination or suspension and the reason(s) for this. The investigator shall then promptly inform the reviewing EC/IRB, if required (please check the regulatory affairs website), and the study subjects and general practitioner. If the EC/IRB decides to suspend or terminate the site the investigator must inform Medtronic immediately.

When the risks are found to outweigh the potential benefits or when there is conclusive proof of definite outcomes, investigators must assess whether to continue, modify or immediately stop the clinical study in the respective investigation site and immediately inform the sponsor and EC/IRB, if applicable.

G.4 Study close out

Study closure is defined as closure of a clinical study that occurs when Medtronic and/or regulatory requirements have been satisfied per the Clinical Investigational Plan and/or by a decision by Medtronic or EC/IRB, whichever occurs first. Study Closure is a process initiated by distribution of a study closure letter. Ethics Board approval renewals are required until the study closure process is complete at the center and the final report submitted. Where applicable, regulator authorities will be notified upon study closure.

H DATA ANALYSIS AND REPORTING

Any deviations from this section will be described and justified in the Final Report/ publication.

H.1 Analysis of clinical data

Each Holter recording will be reviewed for the presence of an abnormal signal (e.g. noise) on the far-field (e.g. RVcoil to SVC) EGM. Only one instance of abnormal noise (e.g. spike) will be needed to classify the recording as abnormal.

The lead from each patient will be adjudicated as a lead failure or intact lead by the physician using routine current practice methods of assessing an ICD lead and recorded on the study exit CRF form. The proportion of Holter recordings with abnormal noise in the lead failure group will be compared with the control group with intact leads. Fisher's exact test will be used to compare the proportions of the 2 independent groups.

Only patients with a good quality Holter recording (minimum 12 hours of telemetry) and a documented assessment of the lead status by the physician will be used in the analysis. Other Holter recordings will not be used.

H.2 Publication Policy

Publications and presentations referring to Therapy coil Electrogram Collection Study will be coordinated by Medtronic to allow the use of all available data. The following publication policy will have to be adhered to by all participating investigation sites:

Medtronic intends to publish the results of the study in a manner that is sensitive to the commercial application of the results. It is likely publication will be delayed until closer to the potential release of a device feature.

Authorship on any publication(s) resulting from this study will be assigned according to substantial contributions to conception and design, acquisition of data, or analysis and interpretation of data, drafting the article or revising it critically for important intellectual content and final approval of the version to be published. This is in accordance with the Vancouver principles (The Uniform Requirements for Manuscripts Submitted to Biomedical Journals: Writing and Editing for Biomedical Publication, ICMJE, October 2008), as agreed upon by the editors of all major medical journals.

The number of authors will be dependent on the regulations of the concerning journal with a maximum of 10 authors. Names of all participating investigators will appear in the Acknowledgment of the paper.

There are no plans to form a publication committee. Publication activities will be assessed after the study is completed and any collaboration with the investigators will be determined at that time.

Based on the principle that Medtronic owns the data of the Therapy coil Electrogram Collection Study a single investigation site may access and use the data provided by itself for scientific publications following prior approval by Medtronic.

Pooling data from several investigation sites for publication purposes, national projects and international projects all require prior approval from Medtronic.

Medtronic as the owner of the data can use the data and/or any results derived from the data or publications based on that data for marketing purposes, further research and development of devices or educational use.

The study sponsor will collect data in such way that no subject can be identified, and monitor study records.

Participating subjects will not be identified by name in any published reports about the study.

I STUDY MANAGEMENT

I.1 Study staff

A list of the sponsor's study staff will be kept under separate cover.

I.2 Advisory committees

I.2.1 Data Monitoring Committee

No Data Monitoring Committee will be installed for this clinical study as no interventions intended to prolong life or reduce risk of a major adverse health outcome (e.g., cardiovascular events) are evaluated, for which favorable or unfavorable study results suggest study

termination. Nor are there safety concerns suggesting the need for a Data Monitoring Committee.

I.3 Records and reports

I.3.1 Investigator records

The investigator is responsible for the preparation (review and signature) and/or retention of the records cited below. All study related information and records are subject to inspection and must be retained for a period of two years after study termination or closure or longer if required by local or hospital regulations, e.g:

- All key correspondence that pertains to the investigation
- Subject's case history records, including: completed CRFs, copy of data collected during study visit, signed and dated subject informed consent form, all relevant observations, observations of serious adverse events, records of reported adverse events, medical history, and documentation of the dates and rationale for any deviation from the Clinical Investigational Plan or Investigator Agreement
- Subject identification and screening log
- Sponsor contact information
- List of participating sites
- The approved Clinical Investigational Plan and any amendments
- Sample patient information and informed consent form
- Insurance certificates
- Signed and dated Investigator Agreement and compensation records
- IRB/MEC approval documents and documentation that the investigator did not participate in the approval process
- Training documentation, current, signed and dated (co-)investigator curriculum vitae, delegated task list and final report
- Any other records that local regulatory agencies require to be maintained

I.3.2 Investigator reporting responsibilities

The investigator is responsible for the preparation (review and signature) and submission to Medtronic of all case report forms and deviations from the clinical investigational plan. If any action is taken by an IRB/MEC with respect to the investigation, the information must be forwarded to Medtronic immediately. Reports are subject to inspection and to the retention requirements as described above for investigator records. The investigator shall prepare and submit in a complete, accurate and timely manner the reports listed in Table 2.

Table 2: Investigator Reports

Report	Submit To	Description / Constraints
Withdrawal of IRB/MEC approval	Medtronic	report as required by local law
Study Deviations	Medtronic, IRB/MEC	Any deviation from the CIP shall be recorded together with an explanation for the deviation. Deviations shall be reported to the sponsor who is responsible for analyzing them and assessing their significance. Note: When relevant, Ethics Boards, competent authorities or the appropriate regulatory bodies should be informed.
Failure to obtain informed consent	Medtronic, IRB/MEC	Notification within five working days.
Progress Reports and final report (if required)	Medtronic, IRB/MEC	Provide if required by local law or Ethics Board

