This is an observational study, no randomization will be used in this study. Evaluation of the EGM signals will be done centrally at Medtronic and the scientist determining the clinical endpoint (i.e. an abnormal EGM noise signature) will be blinded from the lead status during evaluation of the EGMs. Additionally, the physician will be blinded from the scientist's evaluation of the Holter EGM during the study.

C.7 Sample size

It is estimated that a population of 300 patients with the required combination of device and lead exist in Europe. Over a two year period, we expect approximately 50 patients to fulfill the inclusion criteria and provide analyzable Holter data. In the unlikely situation that Holter data from a patient is not analyzable due to signal quality they will be replaced by another patient.

With data from these 50 patients we estimate 10 patients will have a high voltage lead failure of which 5 will have the unique high frequency spike. In the 40 patients without a high voltage lead failure we estimate 1 may also have the unique high frequency spike.

Using a Fisher's exact test, assuming a two-sided alpha of 0.5 we will be able to detect differences with power greater than 80%.

Additionally with an estimated proportion of patients with the unique noise characteristic and a high voltage lead failure of 10%, 50 patients will provide a precision of +/- 7% with a confidence interval of 90%.

C.8 Number of investigation sites and study duration

It is anticipated that two sites will participate in this study. The first site will be the National Institute of Cardiovascular Diseases, Department of Arrhythmias and Cardiac Pacing, Bratislava, Slovakia. The second site will be the Middle Slovakia Institute of Cardiovascular Disease, SUSCCH a.s, Banska Bystrica, Slovakia. These sites were chosen because they have a unique, large pool of patients with Medtronic devices connected to St. Jude Riata leads. A list of investigators will be kept under separate cover.

There will be no upper limit of subject enrollment for each investigator. Once 50 patients with analyzable data have been enrolled the study will stop. There will be no minimum limit that each investigator must enroll, however it is expected that sites will have at least 100 suitable patients (i.e. patients with a Medtronic ICD or CRT-D and St Jude lead) in their referring area.

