We estimate that at least 200 patients will need to be screened to identify at least 50 patients who fulfill the inclusion criteria. Assuming approximately 2 patients presenting per month the study is expected to last 2 years. This estimate will be evaluated after 6 months and modifications to the study may be made if assumptions are inaccurate.

Once patients have fulfilled the inclusion criteria they will be invited to participate in the study. Participation will involve wearing a Holter monitor for 24 hours. A 24 hour Holter is required to allow a sufficient amount of time for an abnormality to be observed on the EGM. One month after the return of the Holter the physician will be asked to complete a study exit form, this form will collect the current status of the lead and information from any additional tests that were performed. The patient is not required to be present when the physician completes the study exit form.

D SUBJECT SELECTION

D.1 Inclusion criteria

- Subject is willing to sign and date the study Informed Consent form
- Subject is at least 18 years of age (or older, if required by local law)
- Subject is willing and able to wear a Holter monitor for up to 24-hours.
- Subject has been implanted with a Medtronic ICD or CRT-D device and a St. Jude Medical Riata or Durata lead and satisfy one of three conditions:

1. Externalized conductor with normal P/S electrical characteristics, or
2. ICD/CRT-D change out and normal P/S electrical characteristics, or
3. Abnormal device diagnostics for high voltage portion of lead
 - Abrupt HV impedance change (more than 75% increase or more than 25% decrease from baseline)
 - Non-physiologic noise on HV EGM
 - Less than 50% of programmed shock energy delivered

D.2 Exclusion criteria

Subjects who meet any of the following exclusion criteria are not eligible to participate in the study:

- Subject has medical conditions that would limit study participation (per physician discretion)
- Subject is enrolled in one or more concurrent studies that would confound the study results of this study as determined by Medtronic

E STUDY PREPARATION PROCEDURES

E.1 Investigator / Investigation site selection

An investigator/investigation site may be included in the investigation if the investigator/investigation site complies with the following requirements:

- Investigator has education / experience in the field of the research (implantable cardiac rhythm devices and cardiac rhythm disturbances)

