2 EGM devices Single and Dual Coil Leads	4 EGM devices Single Coil Lead	4 EGM Devices Dual Coil Lead
Select Parameters>Data Collection Setup> EGM 1: RVtip to RVring EGM 2: Can to RVcoil Press "OK" Press "PROGRAM"	Select Parameters>Data Collection Setup> LECG: RVcoil to Aring EGM 1: RVtip to RVring EGM 2: Can to RVcoil EGM 3: RVtip to RVcoil Press "OK" Press "PROGRAM"	Parameters>Data Collection Setup> LECG: Can to SVC EGM 1: RVtip to RVring EGM 2: RVcoil to SVC EGM 3: Can to RVcoil Press "OK" Press "PROGRAM"

The Holter Telemetry will be turned on for 24 hours

Select Parameters>Data Collection Setup>Select Holter telemetry [24 hours]

Press "PROGRAM"

Note: For wireless telemetry ICD devices select <find patient> then uncheck "Allow Wireless Communication"

The Holter monitor will be attached to the subjects and they will be asked to continue wearing the Holter monitor to record rhythm data for up to 24 hours.

The Holter monitor and the recorded data on the flashcard from the Holter must be returned to the study center. Medtronic will facilitate Holter retrieval for each study participant and this is the end of the study involvement for the patients.

The SD Disks will be sent to Medtronic within 7 working days and at the end of the study the Holvers must be returned to Medtronic. Medtronic will facilitate Holter retrieval from the centers.

F.4 Lead Status and Study Exit Form

One month after the evaluation visit, the physician will be asked to complete a study exit form, this form will collect the current status of the lead and information from any additional tests that were performed during routine clinical practice to determine the status of the lead.

The status of the lead will be classified as intact or failed based on the physician's assessment of the lead with supporting data. The supporting data includes the results of a full output test shock (if performed), returned product analysis (full lead needs to be returned of intact, partial lead can be returned for failure), or device diagnostics (e.g. abnormal high voltage impedance, less than 50% of programmed shock energy delivered for detected episodes).

F.5 Data collection requirements

	Screening	Enrollment	Evaluation Visit	Study Exit
Device and lead Criteria	✓			
Inclusion/Exclusion Criteria		✓		
Subject Informed Consent		✓		
Demographics, device history			✓	
Save-to-disk			✓	
Device Data Collection Settings programmed			✓	
Holter Attached			✓	
Lead Status				✓
Exit				✓

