Study deviations directly related to a subject, including informed consent violations, will be documented in the subject's case history record and recorded on the Deviation CRF. Medtronic will be responsible for analyzing the documented deviations, assessing their significance, and identifying any necessary corrective and/or preventive action. Reporting of deviations must comply with Ethics Board policies, local laws, and or regulatory agency requirements. It is the investigator's obligation to report deviations to IRB/MEC, as required.

F.8.3 Amendments to the Clinical Investigation Plan

Medtronic will submit any significant amendment to the Clinical Investigation Plan, including a justification for this amendment, to the appropriate regulatory authorities and to the investigators to obtain approval from their EC/IRB, if applicable. Administrative amendments to the Clinical Investigation Plan will be submitted to the EC/IRB and appropriate regulatory authorities for notification, if applicable.

G QUALITY CONTROL PROCEDURES

G.1 Procedures for data management

G.1.1 Data collection

The investigator must ensure accuracy, completeness, legibility and timeliness of the data reported in the CRFs and in all other required reports. Data reported on the CRFs which are derived from source documents (e.g. hospital records, laboratory notes or fluoroscopic images) must be consistent with the source documents or the discrepancies need to be justified in a documented rationale, signed and dated by the (principal) investigator, to be filed in the patient medical file.

Only authorized persons can complete CRFs. CRFs shall be signed by investigators (physician) as specified on the Delegated Tasks List included in the Investigator Site File.

In order to maintain an audit trail, changes or corrections in CRFs are made by making a single strike-through on the wrong data and an addition of the correct data. The change in the CRF must be signed, dated, and explained (if necessary) by the person that made the change. If a person only authorized to complete CRFs made changes to an already signed CRF, the investigator shall re-sign this CRF.

Beside the data on the Case Report Forms, save to disk files, Holter files and fluoroscopic images (if available), will also be collected.

All data shall be secured against unauthorized access. The privacy of each subject and confidentiality of his/her information shall be preserved in reports and when publishing any data.

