The study is being conducted in Slovakia at two investigation sites. The first site is the National Institute of Cardiovascular Diseases, Department of Arrhythmias and Cardiac Pacing, Bratislava, Slovakia. The second site is the Middle Slovakia Institute of Cardiovascular Disease, SUSCCH a.s, Banska Bystrica, Slovakia. These sites were chosen because they have a unique, large pool of patients with Medtronic devices connected to St. Jude Riata leads.

All patients will have been previously implanted with an ICD or CRT-D and be attending a routine follow up visit. As part of the study patients will be asked to wear a 24 hour Holter. All treatment decisions will be at the discretion of the physician in accordance with local practice.

The Clinical Investigation Plan V. 2 27 AUG 2014 has been used to develop this Statistical Analysis Plan with the purpose to describe the Final Analysis foreseen for TEC Study.

3. Study Objectives

The primary objective is to report the number of patients with a unique noise characteristic (e.g. high frequency spike) on their Far-field EGM (RV coil to SVC coil or RV coil to Can) and a high voltage lead failure within 1 month.

The secondary objectives of this study are to:

- Compare the proportion of patients with a unique noise characteristic (e.g. high frequency spike) on their Far-field EGM (RV coil to SVC coil) and a high voltage lead failure within 1 month to those patients with a high frequency spike and no lead failure within 1 month.

- Identify additional characteristics in the Far-field EGM (e.g. RV coil to SVC coil) that may help identify patients at risk of a high voltage ICD lead failure.

The clinical endpoint is an abnormal EGM noise signature, one instance of a noise spike during the 24 hour recording will be sufficient to classify the noise signature as present.

4. Investigation Plan

This is a Prospective, non-randomized, multicentre, observational study, no randomization will be used in this study. Evaluation of the EGM signals will be done centrally at Medtronic and the scientist determining the clinical endpoint (i.e. an abnormal EGM noise signature) will be blinded from the lead status during evaluation of the EGMs. Additionally the physician will be blinded from the scientist's evaluation of the Holter EGM during the study. Inclusion/Exclusion criteria are listed below:

Inclusion criteria

- Subject is willing to sign and date the study Informed Consent form

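### The EGM reader is masked to lead status only; the plan does not withhold the entry criterion or the device data that could hint at it

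*Protocol*

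**What the plan says.** **Blinding.** Protocol C.6: "Evaluation of the EGM signals will be done centrally at Medtronic and the scientist determining the clinical endpoint" "will be blinded from the lead status during evaluation of the EGMs". SAP 4 repeats the same scope: "blinded from the lead status during evaluation of the EGMs". In the other direction, "the physician will be blinded from the scientist's evaluation of the Holter EGM during the study". No section masks the inclusion criterion, CRF, device memory or fluoroscopy. None says when the reading is made or when it becomes final.

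**What the sponsor holds.** Protocol G.1.1: besides CRF data, "save to disk files, Holter files and fluoroscopic images (if available), will also be collected". The save-to-disk file holds device settings and memory from the evaluation visit (F.3), and CRFs are submitted to the sponsor (I.3.2).

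**Entry and lead status.** Criterion 3 in Protocol D.1 has three items: an abrupt high-voltage impedance change, "Non-physiologic noise on HV EGM", and "Less than 50% of programmed shock energy delivered". F.4 rests lead status on the physician's assessment. The supporting data are a full-output test shock if one was done, returned product analysis, or "device diagnostics (e.g. abnormal high voltage impedance, less than 50% of programmed shock energy delivered for detected episodes".

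**The reading.** Protocol C.2 and SAP 6.9 define abnormal noise as a departure from the usual waveform and baseline. Low-amplitude myopotentials count as normal, but no amplitude, frequency or duration limit is given. One instance makes a recording positive (also Protocol H.1). No second reader or agreement check is planned.

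**The concern.** The mask covers the physician's verdict but not the information that may point to it. Lead status is recorded one month after the evaluation visit, while the entry reason is known at that visit. The Holter disks go to the sponsor within 7 working days (F.3). If a reading is made during that month, lead status is not yet on record, so masking it withholds little; the entry reason already exists.

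A reader who knew that a patient entered for low delivered energy or an impedance change would have a clue to failure. One who knew that a patient entered for noise on the high-voltage EGM would be primed to find noise. Deciding whether a single deflection in up to 24 hours is a spike or a myopotential leaves room for expectation to act.

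Two results would be exposed. One is the comparison of noise between failed and intact leads, which is the only formal test. The other is the primary count of patients with both noise and failure, which over-calling in failed leads would raise.

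**Working it through.** **1. The plan's own figure.** Inputs from Protocol C.7 and SAP 5: 10 failed leads with 5 spikes (50%), 40 intact leads with 1 spike (2.5%), two-sided Fisher test. I use alpha 0.05 from the SAP. The protocol prints 0.5, which is a separate discrepancy.

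Power = Σx Σy Bin(x; 10, 0.50) × Bin(y; 40, 0.025), summed over tables with Fisher p ≤ 0.05. The result is 95.2%, so the stated power above 80% holds. This point does not affect it.

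**2. How few readings decide the test.** Fisher p for positive readings in failed versus intact leads:

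- 5/10 v 1/40: p = 0.0006
- 3/10 v 1/40: p = 0.022
- 2/10 v 1/40: p = 0.098
- 3/10 v 3/40: p = 0.086

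With one positive reading among intact leads, the third positive among failed leads moves the result across 0.05.

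**3. What expectation could do if noise and failure were unrelated.** The documents give none of these inputs, so all are assumptions:

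- b = 5%: call rate in both groups without any influence.
- c: call rate in criterion 3 patients when the entry reason is known; 15%, 25% or 35%.
- f of 10 failed and g of 40 intact leads entered by criterion 3.

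The number of positive calls is X = Bin(f, c) + Bin(10 − f, b) among failed leads and Y = Bin(g, c) + Bin(40 − g, b) among intact leads. The false-positive rate is Σx Σy P(X = x) × P(Y = y), summed over tables with Fisher p ≤ 0.05. With c = b it is 1.8%, below 5% because the test is conservative at these counts.

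| Criterion 3 entry, failed v intact | c = 15% | c = 25% | c = 35% |
|---|---|---|---|
| 2/10 v 8/40 (equal shares) | 2.0% | 1.9% | 1.6% |
| 5/10 v 20/40 (equal shares) | 2.3% | 2.0% | 1.9% |
| 4/10 v 8/40 | 3.6% | 5.0% | 6.0% |
| 6/10 v 8/40 | 5.8% | 10.2% | 14.7% |
| 8/10 v 8/40 | 8.5% | 17.3% | 26.9% |
| 8/10 v 4/40 | 10.5% | 23.6% | 38.6% |

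The imbalance in criterion 3 entry drives the result. Without it, over-calling adds noise readings to both groups alike and the test keeps its level.

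**4. Effect on the primary count.** Expected positive readings among the 10 failed leads are f × c + (10 − f) × b. At f = 8 this is 10 × 0.05 = 0.5 without influence, and 8 × 0.25 + 2 × 0.05 = 2.1 at c = 25%. The plan expects 5.

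**The case against.** The strongest reply is that silence is not exposure. A reader might infer that the scientist sees the CRFs, device memory and images. The documents do not say so: they say that the sponsor collects them, and receipt by an organisation is not receipt by one scientist. G.1.1 leaves further detail to a Data Management Plan that is not among the documents. This stands. What remains is that C.6 does specify what is masked, and it names lead status alone.

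A reader might also infer that the entry criterion largely determines lead status. That is not supported. Device diagnostics are one of three sources listed in F.4, and no figure gives the share of failures resting on them. Protocol B.1 says that abnormal impedance is often absent and that failures may give no early electrical warning. F.4 names neither noise nor fluoroscopy as evidence of failure; fluoroscopy bears on criterion 1. The overlap is limited to two criterion 3 items, plus the closeness of the third to the endpoint.

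Nor is the comparison unprotected. Reading is central, the reader is masked to the physician's classification, and the physician is masked to the reading. The formal comparison is also a secondary objective in a 50-patient observational study. All of this limits the weight of the point, but none of it covers the entry reason.

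**Conclusion.** The point stands as a gap in the stated scope of masking, not as evidence of bias. The blinding protects the Fisher comparison and the primary count in part. It leaves open a route from entry reason to noise reading that the plan could close.

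The size cannot be known from the documents. With no true association, a 5% baseline and 25% calls in criterion 3 patients, the false-positive rate is about 2% if criterion 3 entry is equally common in both groups. It is 5% at 4/10 v 8/40, 17% at 8/10 v 8/40 and 24% at 8/10 v 4/40. No single value in that range should be quoted as the effect. All of them require that the reader knows the entry reason and is swayed by it.

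**What to change.** Add to Protocol C.6 and SAP 4 that:

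- the scientist receives only the coded Holter file and the EGM channel map needed to read it, since F.3 assigns channels differently by device type and by single- or dual-coil lead;
- the inclusion criterion, CRF, save-to-disk file and fluoroscopic images are withheld from the scientist;
- each noise reading is locked and dated before any of these, or the study exit form, is released to the scientist.

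If readings are already done, the final report should state what the reader had access to when making them.

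The cost is a short addition to each document and a coded-file handover, with no extra patients, visits or procedures. It is a free improvement. It does not remove the separate overlap by which noise on the high-voltage EGM is itself a way into the study.
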